8.1.3 Dose schedule

Insulin glargine/lixisenatide fixed ratio combination (FRC)

The FRC should be self-administered once daily in the morning in the hour (0 to 60 minutes) before breakfast, using Peach Pen or Olive Pen depending on the daily dose of insulin glargine.

Victoza®

Liraglutide (Victoza®) will be administered as per local labelling (such as SmPC in the European Union or PI in the US), continuing the same dose schedule as before randomization. Victoza® can be administered once daily at any time of day, independently of meals.

Byetta®

Exenatide BID (Byetta®) will be administered as per local labelling (such as SmPC in the European Union or PI in the US), continuing the same dose schedule as before randomization. Byetta® can be administered twice daily at any time within the 60 minute period before the morning and evening meal (or two main meals of the day, approximately 6 hours or more apart). Byetta® should not be administered after a meal.

At days of on-site visits, the IMP which is to be administered before breakfast should be self-administered at the investigational site under the observation of site staff.

Bydureon®

Exenatide extended-release (Bydureon®) will be administered as per local labelling (such as SmPC in the European Union or PI in the US), continuing the same dose schedule as before randomization. Bydureon® can be administered once a week at any time of day, independently of meals.

Tanzeum®

Albiglutide (Tanzeum®) will be administered as per local labelling (such as SmPC in the European Union or PI in the US), continuing the same dose schedule as before randomization. Tanzeum® can be administered once a week at any time of day, independently of meals.

Trulicity®

Dulaglutide (Trulicity®) will be administered as per local labelling (such as SmPC in the European Union or PI in the US), continuing the same dose schedule as before randomization. Trulicity® can be administered once a week at any time of day, independently of meals.

Injection site

The IMP should be administered by deep subcutaneous injection, alternating between the left and right anterolateral and left and right posterolateral abdominal wall or thighs or upper arms. Within a given area, location should be changed (rotated) at each time to prevent injection site skin reactions

8.1.4 Starting dose and dose adjustment

8.1.4.1 *Insulin glargine/lixisenatide fixed ratio combination (FRC) group*

Starting dose

Treatment will be initiated with the Peach Pen. The initial daily dose of FRC to be administered will be 10 U: this corresponds to an initial associated dose of 10 U of insulin glargine and 5 µg of lixisenatide according to the 2 U/1 µg fixed ratio used in the Peach Pen.

Patients who are randomized from once weekly formulations of GLP-1 RA to the FRC group must not administer the first dose of FRC until at least 1 week after their last dose of once weekly GLP-1 RA.

Dose adjustment

During the first 8 weeks of treatment, from V3 (Week 0) to V19 (Week 8), the dose will be titrated twice a week as far as possible (see below algorithm in [Table 1](#)) based on the insulin glargine dose, until the patient reaches a target fasting SMPG of 80 to 100 mg/dL (4.4 to 5.6 mmol/L) while avoiding hypoglycemia episodes. Titration will be done at the scheduled weekly visits (V5, V7, V9, V11, V13, V15, V17, V19) plus at one additional weekly titration phone call visit to be scheduled between the weekly visits (V4, V6, V8, V10, V12, V14, V16, V18). The additional titration phone call visit should be scheduled to allow for at least two days in between successive visits (example: weekly visits to occur on Mondays and titration phone calls to occur on Thursdays or Fridays). In case the additional phone call is missed during the week, the titration should continue as per the originally planned schedule. Thereafter, from V19 (Week 8) until V28 (Week 26), the dose will be adjusted as necessary to maintain this fasting SMPG target, with recommendation to evaluate the dose at least once a week. Twice a week titration can be continued if deemed appropriate by the investigator.

During the extension period (Week 26 to Week 52) patients treated with the FRC during the randomized period will continue their FRC treatment with the same dose regimen and dose adjustment algorithm as during the randomized treatment period.

Dose changes are based on the lowest fasting SMPG value from the last 3 measurements, which may include the value measured on the day of titration, measured by the patient using glucometers and accessories supplied by the sponsor. **However, sound clinical judgment is to be exercised during titration and investigators may decide to further up titrate if the lowest value from the last 3 measurements is between 80 and 100 mg/dL but the two other values are well above 100 mg/dL, if they believe that is an appropriate intervention in the best interest of the patient.**

Investigators may adjust or stop titration, or temporarily reduce dose if they believe further titration would be hazardous at that time.

The total daily dose will be capped at 60 U. In case a dose >60 U is needed to maintain glucose parameters below the threshold value defined for rescue therapy, the dose should be kept at 60 U and a rescue therapy should be introduced (see [Section 8.2.3](#) on rescue therapy).

Table 1 - Dose adjustment algorithm for insulin glargine/lixisenatide fixed ratio combination

The lowest fasting SMPG value from the last 3 measurements, which may include the value measured on the day of titration	FRC dose adjustments (U/day)
>140 mg/dL (>7.8 mmol/L)	+4
>100 and ≤140 mg/dL (>5.6 and ≤7.8 mmol/L)	+2
Glycemic target: 80 to 100 mg/dL (4.4 and 5.6 mmol/L), inclusive	No change
≥60 and <80 mg/dL (≥3.3 and <4.4 mmol/L)	-2
<60 mg/dL (<3.3 mmol/L) or occurrence of 2 (or more) symptomatic hypoglycemic episodes or one severe hypoglycemic episode (requiring assistance) documented in the preceding week.	-2 to -4 or at the discretion of the Investigator or medically qualified designee

In the insulin glargine fixed ratio combination group: choice of Peach Pen or Olive Pen

- If the patient needs a FRC dose of 10 to 40 U, use the Peach Pen (insulin glargine/lixisenatide 2:1).
- If the patient needs a FRC dose of 41 to 60 U, use the Olive Pen only (insulin glargine/lixisenatide 3:1).
- Daily doses of FRC higher than 60 U must not be administrated.

In case additional therapy (eg, a dose >60 U is needed to maintain HbA1c below the predefined threshold value (8% at 12 weeks treatment and thereafter)), the dose should be kept at 60 U and a rescue therapy should be introduced (see [Section 8.2.3](#)). All assessments planned at the end of treatment visit (V28 or V35 for the randomized treatment or extension period, respectively) are to be performed before initiating rescue therapy.

Patients will be educated regarding the titration schedule so that they will be able to monitor the titration with the assistance of the Investigator or medically qualified designee. Patients will be allowed to increase the dose by themselves if necessary (ie, if the lowest fasting SMPG value from the preceding 3 measurements, which may include the value measured on the day of titration, is >100 mg/dL), but not more than a maximum dose increase of +2 U and not more often than twice a week. All other dose increases must be discussed between the patient and appropriate site personnel. All discussions must be properly documented in the patient's record. If needed, additional contacts will be made available for patients to discuss dose adjustments in between the scheduled visits. It is at the discretion of the Investigator to allow well-trained patients to make their IMP insulin dose adjustments in between the scheduled visits without prior consultation of the site personnel.

Doses may be reduced or modified at any time for hypoglycemia. Patients who experienced mild to moderate hypoglycemia as a result of a missed meal, unusual exercise or alcohol use will be counseled on the correction of those behaviors and will not necessarily have their insulin dose decreased (decision to be based on Investigator's clinical judgment).

FRC titration monitoring

Data relevant for the FRC dose titration (eg, fasting SMPG, daily insulin dose, hypoglycemia occurrence) will be reviewed by dedicated persons regularly to identify patients whose FRC dose was not titrated according to the recommended dose adjustment algorithm. If needed, re-training of site staff (including investigator) on titration will be performed. The details on FRC titration monitoring will be provided in separate documents.

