The lowest fasting SMPG value from the last 3 measurements, which may include the value measured on the day of titration	FRC dose adjustments (U/day)												
>140 mg/dL (>7.8 mmol/L)	+4												
>100 and ≤140 mg/dL (>5.6 and ≤7.8 mmol/L)	+2												
Glycemic target: 80 to 100 mg/dL (4.4 and 5.6 mmol/L), inclusive	No change												
≥60 and <80 mg/dL (≥3.3 and <4.4 mmol/L)	-2												
<60 mg/dL (<3.3 mmol/L) or occurrence of 2 (or more) symptomatic hypoglycemic episodes or one severe hypoglycemic episode (requiring assistance) documented in the preceding week.	-2 to -4 or at the discretion of the Investigator or designee												

	
approximately 6 hours or more apart). Byetta® should not be administered after a meal.
 
Bydureon®, Tanzeum®, Trulicity® can be administered once a week at any time of day, independently of meals.
 
Dosing
 
Patients randomized to the GLP-1 receptor agonist group will continue the same daily dose and regimen of GLP-1 receptor agonist as prior to randomization.

Noninvestigational medicinal product(s)
 
Background therapy
	
Background therapy: (commercial metformin tablet ± pioglitazone tablet ± SGLT2 inhibitors (canagliflozin, dapagliflozin, empagliflozin)) and rescue therapy will be considered as non-investigational medicinal products (NIMP(s)).
 
Metformin and pioglitazone (if applicable) and SGLT2 inhibitors (if applicable) should be administered according to local product labeling.
 
For metformin, it should be at a stable dose of at least 1500 mg/day or maximal tolerated dose for at least 3 months prior to screening visit (V1). The dose of pioglitazone (if applicable) and SGLT2 inhibitors (if applicable) should also be stable for at least 3 months prior screening visit (V1).
 
The doses of metformin and pioglitazone (if applicable) and SGLT2 inhibitors (if applicable) should be continued and should remain stable throughout the study unless there is a specific safety issue related to this treatment.

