Instruction on how to complete the patient diary on a daily basis will be done by site staff. At each on site visit:

- The study site staff reviews the patient's diary;
- SMPG values stored in the glucose meter memory will be downloaded, printed out, dated, signed and filed into the patient file. This information will help the Investigator to assess treatment effects, adjust insulin doses and compliance.

Note: The SMPG values recorded into the diary, which have to be entered in the e-CRF, have to be checked for consistency with the information downloaded from the glucose meter. In case of inconsistency, the reason for inconsistency has to be documented. If needed, the resulting action (eg, training of the patient on correct documentation of the values) is also to be documented. The confirmed values will be entered into e-CRF by the Investigator or designee based on the glucometer output values.

The patient diary includes but is not limited to the following information:

- Time and dose of IMP (insulin glargine/lixisenatide combination or Victoza®, or Byetta® or Bydureon®, or Tanzeum®, or Trulicity®) injections;
- Days of no IMP use (including date of starting and ending);
- Time and value of fasting SMPG measurements;
- Time of start of meals and SMPG measurements as well as plasma glucose values the days of the 7-point profile;
- Potential changes in background OADs;
- Adverse events, including signs and symptoms suggesting occurrence of hypoglycemia and local injection site reactions, if any;
- Any problems with an injection pen.

9.2.1.2.4 *Body weight*

Body weight should be obtained with the patient wearing undergarments or very light clothing and no shoes, and with an empty bladder. The same scale should be used throughout the study, and calibrated on a regular basis as recommended by the manufacturer.

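### The rule that lets FRC patients raise their own dose looks only at fasting glucose, so it allows +2 U when recent hypoglycemia should send the decision to a clinician

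*Protocol*

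**What the plan says.** All of this is in Protocol section 8.1.4.1 unless stated otherwise.

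- **Self-increase.** "Patients will be allowed to increase the dose by themselves if necessary (ie, if the lowest fasting SMPG value from the preceding 3 measurements" is above 100 mg/dL. The limits are "but not more than a maximum dose increase of +2 U and not more often than twice a week". Only increases other than this one have to be discussed with site personnel.
- **Well-trained patients.** The investigator may let them adjust the dose between scheduled visits "without prior consultation of the site personnel".
- **Table 1, last row.** It applies when the lowest fasting value is below 60 mg/dL, or on "occurrence of 2 (or more) symptomatic hypoglycemic episodes or one severe hypoglycemic episode (requiring assistance) documented in the preceding week". The action is minus "2 to -4 or at the discretion of the Investigator or medically qualified designee". Table 1 in the synopsis has the same row with a slightly different ending: minus "2 to -4 or at the discretion of the Investigator or designee".
- **Monitoring.** "Data relevant for the FRC dose titration (eg, fasting SMPG, daily insulin dose, hypoglycemia occurrence) will be reviewed by dedicated persons regularly", with re-training of site staff if needed.
- **Extension.** The same dose adjustment algorithm continues from Week 26 to Week 52.

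**The concern.** The self-increase sentence defines necessity by one fasting-glucose condition and adds limits on size and frequency. It does not mention hypoglycemia. Table 1 treats recent episodes as a reason to reduce the dose or to bring in a clinician. No sentence says that the hypoglycemia row overrides either the rows for values above 100 mg/dL or the self-increase permission.

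A patient who follows the stated rule could therefore add insulin in a week when the protocol's own algorithm calls for a reduction or a medical decision. What is at stake is patient safety: the patient acts before anyone qualified has looked at the episodes.

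**Working it through.** This is a check of logic, with a little arithmetic on size and timing. The plan gives no figure of its own to reproduce.

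**Step 1. Can both rules apply at once?**

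| | Self-increase | Table 1, last row |
|---|---|---|
| Trigger | Lowest of last 3 fasting values above 100 mg/dL | Lowest fasting value below 60 mg/dL, or the episode criterion |
| Time of day | Before breakfast only | Episodes at any time |
| Look-back | Last 3 fasting measurements | Preceding week |
| Action | Up to +2 U | -2 to -4 U, or clinician's discretion |
| Who decides | Patient | Clinician, where discretion is used |

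The below-60 trigger cannot coincide with a lowest value above 100. The episode trigger can, because it is joined by an *or* and does not depend on the fasting value. For illustration, take fasting values of 110, 115 and 120 mg/dL and two symptomatic daytime episodes in the same week. The self-increase sentence permits +2 U, while the last row of Table 1 gives -2 to -4 U or a clinician's decision.

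**Step 2. How far apart are the two actions?**

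- Against the smaller reduction: +2 - (-2) = 4 U.
- Against the larger reduction: +2 - (-4) = 6 U.
- Against a clinician's decision to leave the dose unchanged: +2 - 0 = 2 U.
- Most that self-increases can add within the one-week look-back: 2 × 2 U = 4 U.
- Relative to the 10 U starting dose, one step is 2/10 = 20%.

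**Step 3. How long can this go without a scheduled contact?** Visit weeks are from the study flow chart (section 1.2).

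- Weeks 0 to 8: two scheduled contacts a week in the FRC arm, so the window is short.
- Weeks 8 to 26: (26 - 8)/2 = 9 intervals of 2 weeks.
- Extension: contacts at Weeks 26, 30, 34, 38, 42, 46 and 50 give 6 intervals × 4 weeks = 24 of the 26 weeks, then 2 weeks to Week 52.

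The exposure therefore lies mainly after Week 8, and most of all in the extension.

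**Step 4. Does anything else in the protocol stop the increase?**

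- Patients are told to contact the site about adverse events (sections 10.1.2.2 and 10.1.3.2). The diary in section 9.2.1.2.3.2 covers "Adverse events, including signs and symptoms suggesting occurrence of hypoglycemia", so this may reach non-severe episodes. It does not suspend the self-increase in the meantime.
- Section 10.6.1 requires prompt site contact after severe events only.
- Scheduled phone visits ask about hypoglycemia and adjust the dose, but a self-increase takes place between them.
- Dose evaluation at least weekly up to Week 26 is a recommendation, not a condition for self-increase.
- The titration review looks for departures from the algorithm after they happen.

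None of these withdraws the permission when the episode criterion is met. The gap is clearest for two or more non-severe episodes.

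**The case against.** The strongest reply is that the sentence should be read with its surroundings. It follows Table 1 directly, and its paragraph opens by saying that patients are educated in the titration schedule and monitor it with clinical assistance. Patients who are taught Table 1 are presumably taught its last row. The delegation is also cautious: +2 U even above 140 mg/dL, where Table 1 gives +4 U. This is a reasonable account of what was meant, but it asks a patient adjusting insulin to infer a stop rule that the stated trigger leaves out.

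Second, a reduction is not mandatory. Table 1 allows discretion, and section 8.1.4.1 adds that mild to moderate episodes explained by a missed meal, exercise or alcohol need not lead to a lower dose. That stands, and it is why the gap may be only 2 U. It also shows that the decision belongs to a clinician, so it does not support the patient acting first.

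Third, there are further safeguards. Investigators may stop titration they consider hazardous. Phone-visit instructions tell patients to inject the prescribed dose. Titration calls must take reported hypoglycemia into account (section 10.1.2.4), and extra calls can be added whenever needed. These make an unreviewed increase less likely but do not prohibit it.

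Finally, the patient titration instruction and the titration-monitoring details are not in the documents. The instruction may already carry the warning. That limits what can be said about practice, but not about the protocol text.

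**Conclusion.** The concern holds. As written, section 8.1.4.1 permits an unsupervised increase of up to 2 U, twice a week, when the episode criterion of Table 1 is met. A single step differs by 4 to 6 U from the tabulated reduction, or by 2 U if the clinician would have kept the dose.

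The documents do not say how many patients would meet both conditions. The number is probably small, because all three recent fasting values must exceed 100 mg/dL in a week with two symptomatic episodes or one severe episode. The 60 U daily cap still applies. The conclusion rests on reading the parenthesis in the self-increase sentence as its full definition of need, and on no unseen patient material supplying the missing condition. It is a patient-safety clarification that should be made; it does not affect any endpoint, estimate or test.

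**What to change.** Add to the self-increase sentence in section 8.1.4.1: *and the hypoglycemia criterion in the last row of Table 1 is not met; if it is met, the patient must not increase the dose and must contact the site.* Apply the same condition to well-trained patients who adjust without consulting the site first. Under Table 1, both in section 8.1.4.1 and in the synopsis, add a note that the hypoglycemia row takes precedence over the glucose rows.

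The cost is one clause and one table note, plus a revised patient titration instruction if the current one lacks the condition. Titration may be slightly slower in a few patients.

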8.2 NON-INVESTIGATIONAL MEDICINAL PRODUCT(S)

8.2.1 Background therapy

Background OAD treatment metformin, pioglitazone and SGLT2 inhibitors (canagliflozin, dapagliflozin, empagliflozin) are considered as non-investigational medicinal products (NIMPs).

Patients are enrolled with a background therapy consisting of metformin alone or metformin and pioglitazone or metformin and SGLT2 inhibitor combination or triple combination. Metformin and pioglitazone (if applicable) and SGLT2 inhibitors (if applicable) should be administered orally according to local product labeling. For metformin, it should be at a stable dose of at least 1500 mg/day or maximal tolerated dose for at least 3 months prior to screening (V1). The dose of pioglitazone (if applicable) and SGLT2 inhibitors (if applicable) should also be stable for at least 3 months prior screening visit (V1). The doses of background OAD treatment should be continued and should remain stable throughout the study unless there is a specific safety issue related to this treatment.

The rescue therapy is also a NIMP and its introduction is described in [Section 8.2.3](#). As per rescue therapy criteria rapid acting insulin is suggested (insulin glulisine when available) for patients in the FRC arm or basal insulin for patients in the GLP-1 RA arm are suggested.

Background therapy or rescue therapy are to be reported in the electronic case report form (e-CRF).

The cost of the permitted background OAD treatment and suggested rescue therapy, if not covered by health insurance, will be reimbursed where permitted by local regulations.

8.2.2 Diet and Exercise

Lifestyle and diet therapy provided before the time of screening is to be continued during the study. Dietary and lifestyle counseling will be given by a healthcare professional at V2 or V3, V21, V28 and V32 which should be consistent with international or local guidelines for type 2 diabetic patients (with regard to the distribution of calories among carbohydrates, proteins, and fats, exercise, etc).

Compliance with the diet and lifestyle counseling will be assessed in case of insufficient glucose control.

8.2.3 Rescue Therapy

In case **HbA1c is above 8% at Week 12 or later on**, the Investigator will receive an alert issued by the central laboratory and should ensure that no reasonable explanation exists for insufficient glucose control and in particular that there is no intercurrent disease which may jeopardize glycemic control (eg, infectious disease), that the treatments are given at the planned dose and compliance to treatment and diet and lifestyle is appropriate. HbA1c assessment should be scheduled at next visit (if next visit is a phone call, it should be replaced by an unscheduled visit at site) or within 4 weeks. If appropriate corrective action fails and if the repeated HbA1c remain above 8%, a rescue therapy should be considered according to the Investigator's judgment.

In the FRC arm:

- rescue therapy is recommended only if further dose titration is not possible, ie, the patient is already at the maximum daily dose of 60 units;
- rapid acting insulin (insulin- glulisine when available) is suggested and should be started as a single daily administration to be given at the main meal of the day (excluding breakfast);
- basal insulin is not allowed in the FRC arm.

In the GLP-1 RA arm:

- suggested rescue therapy is basal insulin at the investigator's discretion.

During the extension period, suggested rescue therapy is rapid acting insulin (insulin- glulisine when available) for all patients.

All assessments planned at the end of the randomized treatment visit (V28) are to be performed before initiating rescue therapy during the randomized treatment period. All assessments planned at the end of extension period treatment visit (V35) are to be performed before initiating rescue therapy during the extension period. After these assessments are completed and rescue therapy initiated, the patient will remain in the study and continue to administer the study treatment (including background therapy). The planned visits and assessments should be performed until the last scheduled visit. Patients receiving rescue therapy during the randomized treatment period and eligible for the extension period can continue it as required.

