9.2 SECONDARY ENDPOINTS

9.2.1 Secondary efficacy endpoint(s)

- Percentage of patients reaching HbA1c <7 % (53 mmol/mol) or ≤6.5% (48 mmol/mol) at Week 26;
- Change in FPG from baseline to Week 26;
- Change in 7-point SMPG profiles from baseline to Week 26 (each time point and average daily value);
- Change in 2-hour PPG and in blood glucose excursion during standardized meal test from baseline to Week 26;
- Percentage of patients requiring rescue therapy during the 26 weeks treatment period;
- Change in body weight from baseline to Week 26.

9.2.1.1 *Observation period of efficacy endpoints*

All scheduled measurements collected during the study period will be used in the analysis, including those obtained after IMP discontinuation or rescue medication use.

For sensitivity analyses, the 26-week on-treatment period is defined as follows:

- For patients who are not eligible to enter the extension period, the 26-week on-treatment period is defined as:
 - For patients receiving daily IMP: the time from the first injection of open-label daily IMP up to 14 days for HbA1c; 0 day for standardized meal test parameters, 7-point SMPG and insulin glargine dose; 1 day for FPG; and 3 days for body weight after the last injection of IMP or up to the introduction of rescue therapy, whichever is the earliest.
 - For patients receiving weekly IMP: The time from the first injection of open-label weekly IMP up to 20 days for HbA1c; 6 day for standardized meal test parameters,

7-point SMPG; 7 day for FPG; and 9 days for body weight after the last injection of IMP or up to the introduction of rescue therapy, whichever is the earliest.

- For patients who are eligible to enter the extension period, the 26-week on-treatment period is defined as the time from the first injection of open-label IMP up to V28/Week 26 visit (or Day 183 if V28/Week 26 visit is missing), or up to the introduction of rescue therapy, whichever is the earliest.

The on-treatment period of the whole study including the 26-week single-arm FRC extension period for efficacy variables is defined as the time from the first injection of open-label IMP up to 14 days for HbA1c; 0 day for standardized meal test parameters, 7-point SMPG and insulin glargine dose; 1 day for FPG; and 3 days for body weight after the last injection of IMP or up to introduction of rescue therapy, whichever is the earliest.

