2.1.3.2 Secondary efficacy endpoint(s)

Continuous secondary efficacy endpoints

The continuous secondary efficacy endpoints are:

- Change in FPG from baseline to Week 26,
- Change in 7-point SMPG profiles from baseline to Week 26 (each time point and average daily value),
- Change in 2-hour PPG and in blood glucose excursion during standardized meal test from baseline to Week 26,
- Change in body weight from baseline to Week 26,

7-point SMPG profiles will be analyzed based on the average of the glucose values recorded on eCRF on 2 different days in the week prior to the scheduled visits.

For 7-point SMPG profiles, the mean daily (ie, average on 7 points) change from baseline to Week 26 will be analyzed. In addition, the change from baseline to Week 26 for each of the 7 points will be evaluated, respectively.

For FPG, only values assessed in fasting condition will be analyzed.

Categorical secondary efficacy endpoints

The categorical secondary efficacy endpoints are:

- Percentage of patients reaching HbA1c $\leq 6.5\%$ (49 mmol/mol) at Week 26,
- Percentage of patients reaching HbA1c $< 7\%$ (53 mmol/mol) at Week 26.
- Percentage of patients requiring rescue therapy during the 26-week randomized treatment period.

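### Rescue is recommended only at 60 U in the FRC arm, with no such condition for control, so a lower FRC rescue rate need not mean less glycaemic failure

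*Protocol*

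**What the plan says.** Protocol 8.2.3 sets one trigger for both arms: a central-laboratory HbA1c above 8% at Week 12 or later, a check for explanations, corrective action, and a repeat test at the next visit or within 4 weeks. Then, "if the repeated HbA1c remain above 8%, a rescue therapy should be considered according to the" investigator's judgment.

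The arms part after that. For FRC, rescue is "recommended only if further dose titration is not possible, ie, the patient is already at the maximum daily dose of 60 units". For the GLP-1 RA arm, "suggested rescue therapy is basal insulin at the investigator's discretion", with no dose condition. SAP 2.1.2.1 repeats both rules. The control dose stays as it was before randomization.

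SAP 2.1.3.2 lists "Percentage of patients requiring rescue therapy during the 26-week randomized treatment period" among the categorical secondary efficacy endpoints, as does Protocol 9.2.1. SAP 2.4.4.2 analyses it by stratified CMH, with a difference in proportions and 95% CI, and adds a Kaplan-Meier curve by arm. SAP 2.5.8 identifies rescued patients from the antidiabetic-medication page of the eCRF, first by the recorded reason and then by a supplementary algorithm. SAP 2.4.4.3 leaves the endpoint outside the testing hierarchy, without multiplicity adjustment.

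On FRC dosing, Protocol 8.1.4.1 makes no change when the lowest of the last three fasting values is 80 to 100 mg/dL, and adds: "Investigators may adjust or stop titration, or temporarily reduce dose if they believe further titration would be hazardous at that time".

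**The concern.** The endpoint counts rescue given. In control that follows from a confirmed HbA1c above 8% plus judgment. In FRC it follows from the same two things plus a dose of 60 U. Two patients with the same confirmed HbA1c can therefore be classified differently because of the arm they are in. If the rule is followed and failure is equal, the extra condition can only lower the FRC percentage.

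The planned difference, CI and curve carry no statement of this, and no planned analysis applies one failure criterion to both arms. A reader of the results would naturally take a lower FRC rescue rate as evidence of better glycaemic control.

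**Working it through.** **The plan's own figure.** No rate, power or sample size is given for the rescue endpoint. The only design figure is 250 per group for HbA1c (Protocol 11.1), and it reproduces. The diluted difference is 0.4 × (1 − 0.20) = 0.32, and n = 2 × (1.960 + 1.282)² × 1.1² / 0.32² ≈ 248.4, so 249 per group. The exact t calculation gives 250, with power 0.901. I use 250 per arm below.

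**Can the 60 U condition bind?** Inputs from Protocol 8.1.4.1: start at 10 U; 16 titration contacts to Week 8 (V4 to V19); dose review at least weekly after that, twice weekly allowed; +2 U for fasting values above 100 and up to 140 mg/dL; +4 U above 140.

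- +2 U at every contact: 10 + 16 × 2 = 42 U at Week 8.
- Weekly +2 U after that: 50 U at Week 12, 58 U at Week 16, 60 U at Week 17.
- +2 U twice weekly throughout: 58 U at Week 12; 25 steps, so 60 U at Week 12.5.
- +4 U at every contact: 13 steps, so 60 U at Week 6.5.
- Fasting target met first: 60 U may never be reached.

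So a patient titrated in +2 U steps is below 60 U at the Week 12 test. With weekly steps after Week 8, the same patient is still below it when a 4-week repeat window closes at Week 16. The condition can bind. How often it does is not in the documents.

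**How large could the effect be?** Let f be the proportion with confirmed HbA1c above 8%, equal in both arms. Let g be the share of FRC failures who reach 60 U and are rescued by Week 26. Assume every qualifying control patient is rescued. Rescue is then f in control and f × g in FRC. Both f and g are assumptions.

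P(reject) ≈ Φ(|p1 − p2| / SE − 1.960), with SE = √{[p1(1 − p1) + p2(1 − p2)] / 250}.

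- f = 10%, g = 0.5 (10% v 5%): SE = √(0.1375 / 250) = 0.02345; 0.05 / 0.02345 = 2.132; Φ(0.172) ≈ 57%.
- f = 10%, g = 0.7 (10% v 7%): SE = √(0.1551 / 250) = 0.02491; 0.03 / 0.02491 = 1.204; Φ(−0.756) ≈ 23% with the small opposite tail.

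Approximate chance of a nominally significant result favouring FRC, by normal approximation and simulation:

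| f | g = 1 | g = 0.75 | g = 0.5 | g = 0.25 |
|---|---|---|---|---|
| 5% | 2.5% | 10% | 31% | 67% to 71% |
| 10% | 2.5% | 17% | 57% | 94% to 95% |
| 20% | 2.5% | 31% | 88% to 89% | over 99% |

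These figures ignore the CMH strata and any patients lost from the mITT population.

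**The case against.** The best defence is that the rule is even-handed in principle: both arms are rescued once randomized treatment cannot be increased. Inclusion criterion I 02 requires the higher comparator dose where two are listed, or the lower if the higher is not well tolerated, and the dose is then fixed. Control patients are thus at their ceiling from the start, while FRC patients reach theirs at 60 U. On that view the endpoint measures need for therapy beyond the regimen, which is a legitimate quantity. This stands, and it is why the endpoint should be kept. It does not make the two criteria the same, and the SAP does not tell the reader which quantity is being compared.

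Four stronger readings are tempting but unsupported.

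- **FRC patients below 60 U are barred from rescue while control patients get it at once.** The FRC condition is worded as a recommendation. Both arms need the checks, the repeat test and the investigator's judgment.
- **A delay in reaching 60 U removes the patient from the count.** The endpoint is cumulative to Week 26. A patient at 60 U by Week 17 can still be rescued after the Week 18 or Week 22 test.
- **The 26-week completers analysis is biased towards FRC by the same rule.** It drops rescued control patients with high HbA1c and can keep comparable FRC patients. That flatters control, so it probably works against FRC.
- **Sections 8.1.4.1 and 8.2.3 contradict each other.** They agree for the patient at 60 U. What remains is a gap below 60 U. It is narrowed because 8.1.4.1 allows up-titration when the lowest value is on target but the other two are well above 100 mg/dL, and because the permission to stop is framed as temporary.

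**Conclusion.** The concern holds in limited form. Rescue eligibility differs by arm, the endpoint counts rescue given, and with equal glycaemic failure the FRC rate can be lower because of the rule. The rescue difference shows need for therapy beyond the regimen and cannot by itself show less glycaemic failure.

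The size is not derivable. The 57% to 23% range rests on three assumptions: 10% failure in both arms, every qualifying control patient rescued, and 50% to 70% of FRC failures reaching 60 U and being rescued. With g = 1 there is no bias. If investigators withhold rescue from some qualifying control patients, the artefact shrinks.

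A reader might infer that the trial's efficacy conclusion is at risk. It is not: the endpoint is outside the hierarchy, and the primary analysis keeps HbA1c values obtained after rescue. What is at stake is the interpretation of one secondary result.

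**What to change.** Keep the protocol endpoint. Replacing it would change the estimand, which the case does not require. In the SAP:

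1. In 2.4.4.2, add a supplementary between-arm comparison (CMH difference with 95% CI, and Kaplan-Meier) of central-laboratory HbA1c above 8% at Week 12 or later, confirmed on repeat, regardless of FRC dose and of whether rescue was started. Admit unscheduled repeat tests. Give a rule for missed repeats and for alerts too late to be confirmed by Week 26, such as one first raised at Week 26.
2. Report rescue received by arm, with the FRC dose at that time, and the number of FRC patients who met the HbA1c trigger but were below 60 U and not rescued.
3. State that rescue eligibility differs by arm and that the rescue difference is not to be read alone as glycaemic efficacy.

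Separately, the sponsor should reconcile Protocol 8.1.4.1 with 8.2.3 for an FRC patient below 60 U with confirmed HbA1c above 8% whose titration has been stopped or whose fasting SMPG is at target. I take no position on what the clinical rule should be.

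The cost is SAP wording and a little more analysis. The alert and repeat test are already required in both arms. The downside for the sponsor is that the rescue difference may look less favourable to FRC beside the common criterion.
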